6.5 Safety analysis

The safety analysis has been included in secondary objective (see 6.2).

6.5.1 Summary statistics

Not applicable.

6.5.2 Statistical inference

Not applicable.

6.6 Demographic and baseline characteristics

Demographic and other baseline characteristics will be summarized and listed. For continuous demographic/baseline variables, results will be summarized and presented as n, number of not available data (NA), mean, standard deviation, median, and minimum and maximum values. For categorical variables, the number and percentage of subjects will be used.

Page 14 of 16 Date: June 04, 2020

Demographic and baseline characteristics variables are:

- Age
- Gender
- Menopausal status
- Race/ethnicity
- ECOG performance status
- TNM staging (tumor, nodules and metastasis)
- Time from diagnosis date to informed consent signature
- Time from metastatic diagnosis date to informed consent signature
- Histological characteristics: Differentiation grade, Ki67 expression, Miotic count, NYHA classification
- Medical and surgical history
- Previous anti-cancer treatments
- Functionality
- Origin of gastrointestinal NET

6.7 Concomitant medications

Concomitant medications associated with an AEs will be coded to the appropriate Anatomical-Therapeutic-Chemical (ATC) code indicating anatomical main group and therapeutic subgroup.

6.8 Statistical significance level

A significance level of 5% will be considered.

Page 15 of 16 Date: June 04, 2020

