#### 20.6 Sample Size and Accrual

Sample size has been calculated using single stage design. For considering Lenvatinib as an effective treatment, a success rate of ORR of at least 25% is expected. However, a success rate of 10% or less would be considered unacceptable. With 90% power and a 5% level of significance, a total of 55 patients for each cohort are required.

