6.1.2 Statistical inference

It is not planned statistical inference.

Page 11 of 16 Date: June 04, 2020

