6.2.2 Statistical inference

Comparisons using log rank test or model of Cox proportional hazards multivariate analysis will be used if needed.

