6.4 Subgroup analysis

Subgroup analysis for ORR, PFS, OS, biochemical response (tumor markers) will be performed outside the indications of the study protocol. The following variables will be part of this analysis to explore differences between subgroups of subjects:

ORR:

- Origin of gastrointestinal NET.
- Functionality.
- Tumor burden (this information will be extract from central radiologic assessment).
- Number of previous lines (1, 2 or 3 lines) (only in pancreatic NET cohort).
- Concomitant use of somatostatin analogues.
- Previous treatment with everolimus or sunitinib (only in pancreatic NET cohort).

PFS:

- Origin of gastrointestinal NET.
- Tumor burden.
- Number of previous lines (1, 2 or 3 lines) (only in pancreatic NET cohort).
- Concomitant use of somatostatin analogues.

Page 12 of 16

Date: June 04, 2020

- Page 13 of 16 Date: June 04, 2020
- Previous treatment with everolimus or sunitinib (only in pancreatic NET cohort).
- o ECOG.
- Prior surgery.
- Age (≤ 65 vs > 65 years).
- o Differentiation grade (G1/G2).
- Radiological response (upon central radiologic assessment).
- OS:
 - Functionality.
 - o Tumor burden.
 - Concomitant use of somatostatin analogues.

Survival curves will be calculated for OS

In addition to the subgroup analysis, it will be calculated:

- Duration of response will be assessed and represented graphically. It will be calculated as time since treatment initiation to progression disease.
- Time to follow-up will be described.

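### The SAP's 5% significance level has no stated scope and no primary test to attach to, so it can fall only on unadjusted secondary, marker and subgroup comparisons

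*SAP*

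**What the plan says.** **Level.** SAP 6.8 consists of one sentence: "A significance level of 5% will be considered". It gives no endpoint, no sidedness and no rule for multiple comparisons. Neither document contains a multiplicity adjustment.

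**Primary endpoint.** Protocol 20.6 sets up a hypothesis for ORR: "Sample size has been calculated using single stage design", with "a success rate of ORR of at least 25% is expected", "a success rate of 10% or less would be considered unacceptable" and "With 90% power and a 5% level of significance, a total of 55 patients for each cohort are required". For the same endpoint, SAP 6.1.2 says: "It is not planned statistical inference".

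**Other analyses.**
- SAP 6.2.2: "Comparisons using log rank test or model of Cox proportional hazards multivariate analysis will be used if needed". The comparisons are not named.
- SAP 6.3 relates a 50% fall in each of three markers (CgA, 5-HIAA, NSE) to PFS by Kaplan-Meier and to radiological response by chi-square or Fisher methods.
- SAP 6.4: "Subgroup analysis for ORR, PFS, OS, biochemical response (tumor markers) will be performed outside the indications of the study protocol". It lists 6 factors for ORR, 10 for PFS and 3 for OS, gives exploration as the purpose, and names no test.
- SAP 6.9 provides for a t test where applicable. Protocol 20.7 allows log-rank or Cox comparisons for PFS and regression models for the primary endpoint.

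**The concern.** The protocol used 5% for one purpose, the per-cohort ORR design. The SAP removes the inference from that endpoint but keeps the 5%, now unrestricted. Followed as written, the trial could call a subgroup, marker or optional survival comparison statistically significant while making no formal statement on the hypothesis it was sized for.

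Those other comparisons are numerous or open in number, they are unadjusted, and the sample size was not set for them. All patients receive lenvatinib, so a difference between subgroups cannot separate a factor that predicts benefit from the drug from one that is merely prognostic. A nominal p below 0.05 on, say, prior everolimus or sunitinib could still be read as predictive.

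**Working it through.** **1. The protocol's own figure.** Inputs from protocol 20.6: null rate 10%, alternative 25%, 5% level, 90% power, single stage. With X ~ Binomial(55, p):

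- P(X ≥ 9 | p = 0.10) = 0.094, above 5%.
- P(X ≥ 10 | p = 0.10) = 0.0444, within 5%.
- P(X ≥ 10 | p = 0.25) = 0.911, above 90%.

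An exact search finds 55 to be the smallest sample size that meets both conditions at one-sided 5%. At one-sided 2.5% the smallest is 64. So 55 reproduces as a one-sided 5% test with success at 10 or more responses (alpha 4.4%, power 91.1%). Neither document states that cut-off or the sidedness.

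**2. Where the 5% in SAP 6.8 can apply.**

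| SAP section | Analysis | Test foreseen? |
|---|---|---|
| 6.1.2 | Primary ORR | No, inference is excluded |
| 6.2.2 | Log-rank or Cox | Optional, number open |
| 6.3 | 3 markers × 2 outcomes = 6 associations | Chi-square/Fisher named for response; Kaplan-Meier for PFS |
| 6.4 | Subgroups | None named |
| 6.9 | t test | Conditional, variable not named |

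**3. Count of subgroup comparisons in SAP 6.4.** Listed pairs of endpoint and factor: 6 + 10 + 3 = 19, built from 11 distinct factors. If each factor is run in every cohort where it applies (tumour origin only in the gastrointestinal cohort; number of previous lines and prior everolimus or sunitinib only in the pancreatic cohort):

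- ORR 5 + 4 = 9
- PFS 9 + 8 = 17
- OS 3 + 3 = 6
- Total 32

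Biochemical response is also named as a subgroup endpoint but has no factor list, so it is not counted.

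**4. Chance of at least one false positive, if every comparison is tested at two-sided 5% and every null is true.** Under independence this is 1 − 0.95^k:

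- k = 19: 1 − 0.377 = 0.623; expected number 19 × 0.05 = 0.95
- k = 32: 1 − 0.194 = 0.806; expected number 32 × 0.05 = 1.6

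The documents give no correlation between tests, so a common correlation between normal test statistics is assumed and varied:

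| Correlation | 19 tests | 32 tests |
|---|---|---|
| 0 | 62% | 81% |
| 0.3 | 53% | 68% |
| 0.5 | 41% | 52% |
| 0.7 | 28% | 35% |
| 0.8 | 22% | 26% |

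**5. Sensitivity to the count.** Treating the 11 distinct factors as independent units gives 1 − 0.95^11 = 43%. Adding the 6 marker associations to the 19 gives 1 − 0.95^25 = 72% under independence. Radiological response as a PFS factor is measured after baseline and is linked to PFS by construction, so a 5% error rate does not describe it; without it, 1 − 0.95^18 = 60%.

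**The case against.** The strongest reply is that the 19 are listed analyses, not planned tests. SAP 6.4 names no test or p-value, gives exploration as its aim, and says openly that the analyses go beyond the protocol. Both documents call the study an exploratory phase II. SAP 6.8 may simply repeat the protocol's design level. This stands in part: the false-positive figures are conditional on testing, and the labelling lowers the severity. It does not settle the matter, because 6.8 exempts nothing, 6.2.2 has no exploratory wording, and the one analysis to which a repeated design level would belong has its inference excluded by 6.1.2.

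A reader might also infer stronger claims that the documents do not support:

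- *That the subgroup and log-rank or Cox comparisons are the only significance tests.* They are not. SAP 6.3 and 6.9 and protocol 20.7 provide for others.
- *That a false positive is likely.* That depends on correlation. The same 11 factors recur over related endpoints in the same patients, and for 19 tests the chance is below one half at a correlation of 0.5 or more.
- *That the subgroup list was chosen with results known, because SAP version 2.0 is dated June 2020.* The SAP's calendar dates are headed as estimates and match the protocol's projections. They do not show when visits or reports took place. No earlier SAP version is among the documents, so analyses added in version 2.0 cannot be identified.
- *That the two cohorts will be tested against each other.* No section plans this. The cohorts are described as independent, and ORR, early tumour shrinkage, depth of response and safety are all reported by cohort.

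**Conclusion.** The concern holds in a limited form. The 5% level is unscoped and unadjusted, and under the SAP as written it can be used only for analyses other than the hypothesis that fixed the sample size. If all the listed subgroup comparisons were tested at that level, the chance of at least one false positive would be 22% to 62% for 19 tests and 26% to 81% for 32. Even the low end is more than four times 5%. These ranges assume two-sided tests, all nulls true and a common correlation between 0.8 and 0; they do not predict what the trial will report. The mismatch between protocol 20.6 and SAP 6.1.2 rests on none of these assumptions and is the firmer part of the point. The exploratory setting makes this a change that should be made, not a fatal flaw.

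**What to change.** 1. **SAP 6.8:** state that the 5% level applies to the ORR hypothesis in each cohort, and give the side.
2. **SAP 6.1.2:** replace the exclusion of inference with that test. The protocol's inputs correspond to an exact one-sided 5% binomial test of 10%, with success at 10 or more responses of 55 per cohort (alpha 4.4%, power 91.1%). Without this change, step 1 would leave the 5% level attached to no test.
3. **SAP 6.2.2, 6.3 and 6.4:** report within-cohort estimates with 95% confidence intervals (ORR by subgroup; hazard ratios for PFS and OS). Label them exploratory and, for 6.4, not specified in the protocol. Mark any p-value as nominal and unadjusted.
4. **SAP 6.2.2:** replace the open condition with a list of named within-cohort comparisons.

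The cost is SAP wording, one added primary analysis per cohort and table footnotes; no new data are needed. The downside is that subgroup and marker results could no longer be called statistically significant.

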6.9 Statistical model assumptions

The following assumptions will be verifying to guarantee t Student test (if applicable)

- Normality of data
- Variance homogeneity
- Independence in data

In case of applying a Cox regression model, proportional hazards assumption (graphically) will be checked.

6.10 Transformation of expected variables

• The ORR is defined as the proportion of subjects who have best overall response of CR or PR (by RECIST 1.1):

- The time to progression is defined as the difference between start of drug (C1D1) and the progression date or death (whichever occurs first) or the last tumor assessment documented.
- ETS rate is defined as 20% reduction in target lesions after the first 6 weeks of treatment.
- DpR is defined as percentage of maximum tumor shrinkage observed at the nadir (the minimum of total sum of diameters) compared with baseline.
- Overall survival is defined as the time from the start of drug (C1D1) to death.

6.11 Handling of missing data

No planned procedure of imputation of missing values. The analysis will be performed with the available data.

6.12 Description of the softwares to be used for data analysis

Statistical programming and analyses will be performed using R [2] statistical software.

6.13 Interim analysis protocol

The interim analysis will be performed when the last patient included in the corresponding cohort of the study will have at least two tumor assessments (12 weeks after the last patient recruited).

Page 16 of 16 Date: June 04, 2020

7. References

- 1. Guidance for Industry: Clinical Trail Endpoints the Approval of Cancer Drugs and Biologics (May 2007).
- 2. R Core Team (2015). R: A language and environment for statistical computing. R Foundation for Statistical Computing, Vienna, Austria. URL (http://www.R-project.org/).
